8.9 ASSESSMENT OF SAFETY

8.9.1 SPECIFICATION OF SAFETY VARIABLES

Safety assessments will consist of monitoring all adverse events and reporting adverse events (AEs) and serious adverse events (SAEs) that are considered related to **pembrolizumab**, all events of death, and any study specific issue of concern.

8.9.1.1 Adverse Events

An AE is any unfavorable and unintended sign, symptom, or disease temporally associated with the use of an investigational (medicinal) product or other protocol-imposed intervention, regardless of attribution.

This includes the following:

• AEs not previously observed in the subject that emerge during the protocol-specified AE reporting period, including signs or symptoms associated with advanced recurrent endometrial carcinoma that were not present prior to the AE reporting period.

- Complications that occur as a result of protocol-mandated interventions (e.g., invasive procedures such as cardiac catheterizations).
- If applicable, AEs that occur prior to assignment of study treatment associated with medication washout, no treatment run-in, or other protocol-mandated intervention.
- Preexisting medical conditions (other than the condition being studied) judged by the investigator to have worsened in severity or frequency or changed in character during the protocol-specified AE reporting period.

8.9.2 Serious Adverse Events

Refer to Section 9.0 of the study protocol.

8.9.3 Methods and Timing for Assessing and Recording Safety Variables

The investigator is responsible for ensuring that all AEs and SAEs that are observed or reported during the study, as outlined in Section 9, are collected and reported to the appropriate IRB(s), and Merck in accordance with FDA regulations at 21CFR 312.32 (a)(IND Safety Reports).

8.9.4 Adverse Event Reporting Period

The study period during which all AEs and SAEs must be reported begins after informed consent is obtained and initiation of study treatment and ends 30 days following the last administration of study treatment or study discontinuation/termination, whichever is earlier. After this period, investigators should only report SAEs that are attributed to prior study treatment.

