4.8 Subject Withdrawal/Discontinuation Criteria

Subjects may withdraw consent at any time for any reason or be dropped from the trial at the discretion of the investigator should any untoward effect occur. In addition, a subject may be withdrawn by the investigator or the Sponsor if enrollment into the trial is inappropriate, the trial plan is violated, or for administrative and/or other safety reasons.

A subject must be discontinued from the trial for any of the following reasons:

• The subject or legal representative (such as a parent or legal guardian) withdraws consent. Version 9.0, 26 April 2023

- Confirmed radiographic disease progression
- Intercurrent illness that prevents further administration of treatment
- Investigator's decision to withdraw the subject
- The subject has a confirmed positive serum pregnancy test
- Noncompliance with trial treatment or procedure requirements
- The subject is lost to follow-up
- Completed 24 months of uninterrupted treatment with pembrolizumab or 35 administrations of study medication, whichever is later.

Note: 24 months of study medication is calculated from the date of first dose. Subjects who stop pembrolizumab after 24 months may be eligible for up to one year of additional study treatment if they progress after stopping study treatment.

- Administrative reasons
- In case of radiographic complete response confirmed with 2 consecutive CAT scans 12 weeks apart, patient may be discontinued from study.

After the end of treatment, each subject will be followed for 30 days for adverse event monitoring (serious adverse events will be collected for 90 days after the end of treatment). Subjects who discontinue for reasons other than progressive disease will have post-treatment follow-up for disease status until disease progression, initiating a non-study cancer treatment, withdrawing consent or becoming lost to follow-up. After documented disease progression each subject will be followed by telephone for overall survival until death, withdrawal of consent, or the end of the study, whichever occurs first.

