Note: In order to more precisely determine time of progression, the investigator is encouraged to obtain radiologic assessments earlier than 12 weeks if there is a strong clinical suspicion of progression of disease to either confirm or refute the clinical impression.

End-of- Treatment Visit:

- Physical examination will be performed. A pelvic examination is required if this method is used to measure your disease.
 - A CT scan of the chest, abdomen and pelvis will be performed, if not done within prior 12 weeks.
 - Blood test for CBC, Chemistry,

Follow-up:

Subjects will need to see their doctor every 3 months to check the status of their disease for 2 years following study treatment. Afterwards, they will see the doctor every 6 months for 3 years and then yearly.

Patients who have completed study treatment or who have discontinued study treatment for reasons other than Progressive Disease per RECIST 1.1 will continue to be evaluated with tumor assessments every 12 weeks (+/-14 days) until documentation of Progressive Disease, withdrawal of consent or until the patient starts subsequent anti-cancer therapy, whichever comes first.

Patients will be followed every 3 months for survival only after disease progression. This may be performed by telephone follow up.

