6.1.1.5.3 Subsequent Anti-Cancer Therapy Status

The investigator or qualified designee will review all new anti-neoplastic therapy initiated after the last dose of trial treatment. If a subject initiates a new anti-cancer therapy within 30 days after the last dose of trial treatment, the 30 day Safety Follow-up visit must occur before the first dose of the new therapy. Once new anti-cancer therapy has been initiated the subject will move into survival follow-up.

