6.1.1.6 Adverse Event (AE) Monitoring

The investigator or qualified designee will assess each subject to evaluate for potential new or worsening AEs as specified in the Trial Flow Chart and more frequently if clinically indicated. Adverse experiences will be graded and recorded throughout the study and during the follow-up period according to NCI CTCAE Version 4.0. Toxicities will be characterized in terms regarding seriousness, causality, toxicity grading, and action taken with regard to trial treatment.

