11.4 Study Monitoring of Primary Objectives

There will be one formal futility interim analysis for treatment efficacy in the study.

If the study has an accrual of 12 eligible and evaluable patients in the first stage since the study is activated, which is permitted to range from 8 to 15, the accrual of the study will be temporarily suspended until the data of primary endpoint is matured to make a decision on whether to go forward to second stage accrual according to the guidelines. That is, if there are 0 out of 8-13 or at most 1 out of 14-15 patients responding (complete or partial response) and medical judgment indicates, the study will be stopped and the treatment will be classified as clinically uninteresting. Otherwise, accrual to the second stage of the trial will be initiated. As this is a two-stage multi-institutional phase II protocol, the initial overall review of toxicity is usually performed after completion of the first stage of accrual, at which point accrual is generally suspended pending formal analysis of response.

Accrual Goal

The projected minimum and maximum accruals for the study are 8 and 25 eligible and evaluable patients, respectively. The targeted accrual is 12 eligible and evaluable patients in the first stage of the study, and cumulatively 22 eligible and evaluable patients will be targeted in the second stage if the study advances.

Study Duration

1) Patients will receive therapy until disease progression or intolerable toxicity intervenes.

The patient can refuse the study treatment at any time.

2) All patients will be treated (with completion of all required case report forms) until disease progression, initiation of a subsequent cancer treatment or study withdrawal.

Patients will then be followed every three months for the first two years and then every six months for the next three years.

3) A patient is considered off study therapy when the patient has progressed or died, a nonprotocol drug or therapy (directed at the disease) is initiated, or all study therapy is discontinued. Report all treatment received on Cycle Drug Information Forms and adverse events on Adverse Events Forms until the patient qualifies as being off study therapy.

Estimated Duration for Completion of Primary Endpoint: provision of timeframe, e.g. 24 months from activation

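### The rules feeding the primary toxicity table conflict: event windows differ between 4.8, 8.9.4 and 11.4, and 11.2 drops dosed patients later found ineligible

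*Combined protocol and SAP*

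**What the plan says.** Toxicity graded by CTCAE is a primary objective (1.1.2) and the second listed primary endpoint (11.1). Section 11.2 plans a descriptive frequency table for it, without a test or threshold.

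These passages govern which events reach that table:

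- Section 4.8 monitors AEs for 30 days, and states that "serious adverse events will be collected for 90 days after the end of treatment". It sets no attribution condition.
- Section 8.9.4 says the period for reporting all AEs and SAEs "ends 30 days following the last administration of study treatment or study discontinuation/termination, whichever is earlier". After that, only SAEs attributed to earlier study treatment are reported.
- Section 11.4, under Study Duration, asks for "adverse events on Adverse Events Forms until the patient qualifies as being off study therapy". It defines the cut-off so: "A patient is considered off study therapy when the patient has progressed or died". A new anticancer therapy, or the end of all study therapy, also counts.
- Section 6.1.1.6 says: "Adverse experiences will be graded and recorded throughout the study and during the follow-up period". That follow-up period is not defined.
- Section 7 classes toxicity as acute up to 30 days from treatment completion and as chronic after that.

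On who is counted, 11.2 first says that everyone given any study therapy is evaluated for efficacy and toxicity. It then removes from the analysis those who received no therapy and those judged ineligible. It does not exempt ineligible patients who were dosed, and it names no separate safety set.

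**The concern.** A frequency table needs a fixed window and a fixed denominator, and the plan settles neither. Two analysts working from the same protocol could build different tables for a primary endpoint. Following 11.4 literally leaves out events that 4.8 says are to be followed. Following 8.9.4 leaves out SAEs that 4.8 says are to be collected. Following the second sentence of 11.2 leaves out patients who took the drug.

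The timing matters for this drug by the protocol's own account: section 4.2.2 warns that immune-related events can appear months after the last dose.

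**Working it through.** **The plan's own calculated figures.** Inputs are Table 8 (stop at 0 responses for 8-13 patients or 1 for 14-15; reject at 1 for 18 or 2 for 19-25) and response rates of 5% and 25%. For each pair of stage 1 size n1 and final size n, with stage limits r1 and r2:

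- early termination = P(X1 ≤ r1)
- declared interesting = sum over x > r1 of P(X1 = x) × P(X2 > r2 − x), where X2 is binomial on n − n1 patients

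Averaged over the 8 × 8 = 64 pairs, this gives alpha 9.45% (stated 9.5%), power 90.05% (90.0%), early termination 64.89% (64.9%) and expected size 15.13 (15.14). These agree with 11.3 apart from a difference of 0.01 in expected size. No AE window enters the calculation, so the window conflict cannot change it.

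**The capture rules side by side.**

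| Section | AEs after treatment | SAEs after treatment | Anchor |
|---|---|---|---|
| 4.8 | 30 days | 90 days, any attribution | end of treatment |
| 8.9.4 | at most 30 days | at most 30 days for all, then attributed only | last dose or study discontinuation |
| 11.4 | none past the off-therapy date | no separate rule | off-therapy date |
| 6.1.1.6 | undefined follow-up period | undefined follow-up period | none |

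**Case 1: a non-fatal SAE, not attributed to drug, 60 days after last dose.** Under 4.8 it is collected, since 60 ≤ 90. If end of treatment is dated later than last dose, it is still inside. Under 8.9.4 it falls outside, since 60 > 30 and it is unattributed. This holds on either reading of the last clause of 8.9.4, because neither extends the period past 30 days after last dose.

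**Case 2: a non-serious AE between off-therapy and day 30.** Let k be the days from last dose to the off-therapy date. If 4.8's end of treatment means last dose, 4.8 follows AEs to day 30 and 11.4 stops at day k, so the gap is 30 − k days when k < 30 and zero otherwise. If it means the off-therapy date, the gap is the full 30 days. The gap therefore runs from 0 to 30 days. The documents fix neither k nor the anchor.

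**Case 3: a non-serious AE more than 30 days after treatment completion.** Section 7 would class it as chronic. None of 4.8, 8.9.4 and 11.4 collects it, so the chronic class has no systematic non-serious data.

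**Safety set.** Each dosed patient removed is 1/25 = 4.0% of the maximum accrual, or 1/22 = 4.5% of the target. As an illustration (the documents give no ineligibility rate), suppose 22 patients without a given SAE and one dosed patient with it who is later ruled ineligible: 1/23 = 4.3% becomes 0/22 = 0%. Rates can also rise: removing a patient without the event turns 5/25 = 20.0% into 5/24 = 20.8%.

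**The case against.** The best defence is that little is lost. The table is descriptive, in at most 25 patients. Objective 1.1.2 concerns toxicity of pembrolizumab, and 8.9.1 directs reporting to related events and deaths. Attributed late SAEs stay reportable under 8.9.4 and 8.10.2 f. Eligibility is verified before a study number is issued (10.4), so late ineligibility should be uncommon. Training, a shared database and monitoring (10.2 and 10.3) may keep sites consistent. All of this limits the size of the problem, but none of it says which rule applies. Nor does the contrast between collecting (4.8) and reporting (8.9.4) help, because the plan defines no separate data streams and does not say which one feeds 11.2. Section 9.2 asks collaborating sites for serious unexpected events whatever their attribution, but it sets no period.

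A reader might infer more than the text supports:

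- **8.9.4 closes on the day of progression.** Section 4.8 says "A subject must be discontinued from the trial for any of the following reasons" and lists confirmed progression. But the clause in 8.9.4 can equally mean 30 days after the earlier of last dose and discontinuation, and 4.8 itself goes on following these patients for AEs and SAEs.
- **A fixed number of days is always lost under 11.4.** Section 4.2.2 allows up to 12 weeks from last dose for a toxicity to resolve before treatment is discontinued, so k can exceed 30 and the gap can vanish.
- **6.1.1.6 is a further cut-off.** It gives none. Its follow-up period could be the safety follow-up implied by "the 30 day Safety Follow-up visit must occur before the first dose of the new therapy" in 6.1.1.5.3, and section 6 says "Patients will be followed every 3 months for survival only after disease progression". This is an ambiguity.
- **The 30-day safety visit is missing.** Table 6 has an end-of-treatment visit with toxicity evaluation, and 4.8 separately requires 30 days of AE monitoring.
- **Exclusions reverse the response decision.** Section 4.9 replaces ineligible patients, the design is stated for eligible and evaluable patients, and no ineligibility rate is given.
- **4.9 and 4.10 contradict each other on replacement.** One covers ineligible patients and those who drop out before treatment; the other covers discontinuation.

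**Conclusion.** The concern holds in three specific places. First, 4.8 collects all SAEs to 90 days, while 8.9.4 stops no later than 30 days after last dose and then takes only attributed ones. Second, 11.4 ends AE forms at off-therapy, although 4.8 requires 30 days of AE follow-up. Third, the two sentences of 11.2 disagree about dosed patients who are ineligible.

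The events at risk are non-fatal, unattributed SAEs on days 31-90 and AEs between off-therapy and day 30, a gap of 0 to 30 days. The documents give no event rate for these intervals, so no event count is claimed. Each dosed patient excluded is 4.0% of 25. Alpha, power and the Table 8 rule do not depend on the AE windows. The conclusion rests on the current wording alone. It should be corrected because it affects a primary-endpoint table, but it does not threaten the response conclusion.

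**What to change.** Reconcile 4.8, 8.9.4, 11.4 and 6.1.1.6 to one AE window and one SAE window, counted from one anchor date, with the SAE attribution rule stated. Which window to adopt is for the sponsor and investigators; this note does not choose. In 11.2, name the window that feeds the toxicity table and say what section 7's chronic class can contain.

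Analyse toxicity in every patient who receives any pembrolizumab. Keep the eligible-and-evaluable set for the response rule, with indeterminate patients in the denominator as 11.2 already provides. An all-treated response proportion could be added as one sensitivity line.

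The cost is wording in the listed sections and perhaps a few more events in the table. The trial summary gives June 2020 as the planned end, and this version is dated April 2023. If collection is over, new wording cannot recover events that were never recorded, and the report should state the window and the analysis set actually applied.

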8.9.5 Assessment of Adverse Events

All AEs and SAEs whether volunteered by the subject, discovered by study personnel during questioning, or detected through physical examination, laboratory test, or other means will be reported appropriately.

Each reported AE or SAE will be described by its duration (i.e., start and end dates), regulatory seriousness criteria if applicable, suspected relationship to pembrolizumab (see following guidance), and actions taken.

To ensure consistency of AE and SAE causality assessments, investigators should apply the following general guideline:

Yes

There is a plausible temporal relationship between the onset of the AE and administration of pembrolizumab and the AE cannot be readily explained by the subject's clinical state, intercurrent illness, or concomitant therapies; and/or the AE follows a known pattern of response to pembrolizumab and/or the AE abates or resolves upon discontinuation of pembrolizumab or dose reduction and, if applicable, reappears upon re-challenge.

No

Evidence exists that the AE has an etiology other than pembrolizumab (e.g., preexisting medical condition, underlying disease, intercurrent illness, or concomitant medication); and/or the AE has no plausible temporal relationship to pembrolizumab administration (e.g., cancer diagnosed 2 days after first dose of study drug).

Expected adverse events are those adverse events that are **listed** or characterized in the Package Insert or current Investigator Brochure.

Unexpected adverse events are those **not listed** in the Package Insert (P.I.) or current Investigator Brochure (I.B.) or not identified. This includes adverse events for which the specificity or severity is not consistent with the description in the P.I. or I.B. For example, under this definition, hepatic necrosis would be unexpected if the P.I. or I.B. only referred to elevated hepatic enzymes or hepatitis.

8.10 PROCEDURES FOR ELICITING AND RECORDING ADVERSE EVENTS

8.10.1 Eliciting Adverse Events

A consistent methodology for eliciting AEs at all subject evaluation time points should be adopted. Examples of non-directive questions include:

"How have you felt since your last clinical visit?

"Have you had any new or changed health problems since you were last here?"

8.10.2 Specific Instructions for Recording Adverse Events

Investigators should use correct medical terminology/concepts when reporting AEs or SAEs. Avoid colloquialisms and abbreviations. All information will be recording using Oncore Clinical Trials Management System.

a. Diagnosis vs. Signs and Symptoms

If known at the time of reporting, a diagnosis should be reported rather than individual signs and symptoms (e.g., record only liver failure or hepatitis rather than jaundice, asterixis, and elevated transaminases). However, if a constellation of signs and/or symptoms cannot be medically characterized as a single diagnosis or syndrome at the time of reporting, it is ok to report the information that is currently available. If a diagnosis is subsequently established, it should be reported as follow-up information.

b. Deaths

All deaths that occur during the conduct of the research must be reported to the Yale Principal Investigator and the Remote Monitoring Coordinator immediately (if possible) to ensure that all over site committees are properly informed. All information will be entered into Oncore Clinical Trials Management System and updated appropriately. Further determination regarding the need to submit to the subjects local IRB, Yale University HHRP following IRB Policy 710 for reporting Unanticipated Problems Involving Risk to Subjects and Merck Pharmaceuticals, Inc. Drug Safety Committee will be

reviewed.

When recording a death, the event or condition that caused or contributed to the fatal outcome should be reported as the single medical concept. If the cause of death is unknown and cannot be ascertained at the time of reporting, report "Unexplained Death".

c. Preexisting Medical Conditions

A preexisting medical condition is one that is present at the start of the study. Such conditions should be reported as medical and surgical history.

A preexisting medical condition should be re-assessed throughout the trial and reported as an AE or SAE only if the frequency, severity, or character of the condition worsens during the study. When reporting such events, it is important to convey the concept that the preexisting condition has changed by including applicable descriptors (e.g., "more frequent headaches").

d. Hospitalizations for Medical or Surgical Procedures

Any AE that results in hospitalization or prolonged hospitalization should be documented and reported as an SAE.

If a subject is hospitalized to undergo a medical or surgical procedure as a result of an AE, the event responsible for the procedure, not the procedure itself, should be reported as the SAE. For example, if a subject is hospitalized to undergo coronary bypass surgery, record the heart condition that necessitated the bypass as the SAE.

Hospitalizations for the following reasons do not require reporting:

Hospitalization or prolonged hospitalization for diagnostic or elective surgical procedures for preexisting conditions

Hospitalization or prolonged hospitalization required to allow efficacy measurement for the study or

Hospitalization or prolonged hospitalization for scheduled therapy of the target disease of the study.

e. Pregnancy

If a female subject becomes pregnant while receiving investigational therapy or within 30 days of awareness after the last dose of study drug, a report should be completed and expeditiously submitted to Merck Pharmaceuticals, Inc. Follow-up to obtain the outcome of the pregnancy should also occur.

Abortion, whether accidental, therapeutic, or spontaneous, should always be classified as serious, and

expeditiously reported as an SAE. Similarly, any congenital anomaly/birth defect in a child born to a female subject exposed to pembrolizumab should be reported as an SAE. A negative pregnancy outcomes should be reported to Merck as SAE.

f. Post-Study Adverse Events

The investigator should expeditiously report any SAE occurring after a subject has completed or discontinued study participation if attributed to prior pembrolizumab exposure.

If the investigator should become aware of the development of cancer or a congenital anomaly in a subsequently conceived offspring of a female subject who participated in the study, this should be reported as an SAE.

g. Reconciliation

Sponsor is responsible to monitor successful transmission of SAE reports to Merck.

